## 10.6.2. Pharmacodynamic Assessments

### 10.6.2.1. dAXP

Venous blood samples for the determination of total erythrocyte dAXP (EDTA tube, 2 mL per timepoint) will be collected at the timepoints listed in Appendix 2. Samples will be collected, processed and shipped to the central laboratory for analysis as described in the laboratory manual for the study.

### 10.6.2.2. Maximum Total Blood Collection Volume

During a patient's study participation, the maximum amounts of venous blood that will be collected are listed in Appendix 2. Note: there is limited PK sampling for patients < 10 years of age.

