## 10.6. Pharmacokinetic and Pharmacodynamic Assessments

### 10.6.1. Pharmacokinetic Assessments

Only patients  $\geq 10$  years of age will undergo full PK assessments due to blood volume restrictions in pediatric patients. All patients  $< 10$  years of age will have the same assessments and in lieu of full PK sampling will have limited PK sampling done. Only trough samples along with 48 hours post dose during Adagen Lead In Week T-5 and EZN-2279 Week T-9 will be collected.

Venous blood samples (EDTA tube, up to 2 mL per timepoint) for the determination of the PK profile of EZN-2279 will be collected at Week L-4, after the Adagen® lead-in, and Week T-9 after initiation of EZN-2279 therapy (see Appendix 2). Note: If the dose of EZN-2279 is altered, the full PK profile should be repeated not earlier than 4 weeks after adjustment of the dose of EZN-2279.

**Note:** The site should calculate sample collection dates and times in advance of scheduling a patient's first day of administration, so as to avoid sample collections during non-routine times such as evenings, holidays, etc.

It is extremely important to collect all samples at the times specified. Both the scheduled and actual times of sample collection should appear on the sample collection record used in the clinic. In addition, the actual times at which the infusion is started and stopped must be recorded.

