### 11.3.8.1. EZN-2279 Dose Evaluation for Adjustment

The results from trough ADA activity and dAXP will be reviewed to assess whether patients have a dAXP level  $\leq 0.02$   $\mu\text{mol/mL}$  and a trough ADA activity level  $\geq 15$   $\mu\text{mol/h/mL}$ .

Based upon this review:

- If the Week T-7 and T-8 values for ADA activity and dAXP levels meet the established values, the patient will proceed to Day 57 (Week T-9) and begin full PK sampling
- If the Week T-7 and T-8 values for ADA activity and dAXP levels **DO NOT** meet the established values and the patient is not considered fully detoxified:
  - The patient will have his/her dosage of EZN-2279 adjusted. Dose adjustments will be based upon dAXP and ADA values and agreed upon by the PI, Sponsor and Lead PI
  - Return to Week T-5 (Section 11.3.5) and continue through weekly dosing for 4 weeks (T-5 through T-8) and be re-assessed as described in this section

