### 11.3.10. Days 58 through 63 (Week T-9)

The patient will return to the study site each day for blood sampling (only for patients  $\geq 10$  years of age). Blood samples for ADA activity will be obtained at 24, 48, 72, 96, 120, 144, and 168 hours following Day 29 dose. All blood samples will be obtained  $\pm 4$  hours of the scheduled collection time. Note: the 168 hour post-dose sample will be obtained immediately prior to the Week T-10 dose of EZN-2279.

For patients < 10 years of age, PK sampling will be limited to trough samples and at 48 hours post dose for monitoring of ADA activity and Cmax timepoint.

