## Appendix 2. Blood Sampling Schedule and Collection Volumes

| Test:  | Routine Safety         |                           | Study Assessments |                 |                 |                 |              |                 | Total*                               |                                      |
|--|------------------------|---------------------------|-------------------|-----------------|-----------------|-----------------|--------------|-----------------|--------------------------------------|--------------------------------------|
|  | Hematology (incl. ALC) | Chemistry                 | dAXP*             | Trough ADA*     | Full PK ADA     | Immunogenicity* | Quant. Ig    | Lymph subset    |                                      |                                      |
| Volume per Sample (mL)                         | 3                      | 4                         | 2                 | 2               | 2               | 2               | 3.5          | 4               | Patient
s ≥ 10
years
of age | Patient
s < 10
years
of age |
| Tube Type                                      | EDTA (lavender)        | Gel separator (tiger top) | EDTA (lavender)   | EDTA (lavender) | EDTA (lavender) | EDTA (lavender) | Gold top SST | EDTA (lavender) |                                      |                                      |
| Study Days                              |                        |                           |                   |                 |                 |                 |              |                 |                                      |                                      |
| Screening                                      | 3                      | 4                         |                   |                 |                 | 2               |              |                 | 9                                    | 9                                    |
| Adagen® Patients on 1x week dosing only |                        |                           | 2                 | 2               |                 |                 |              |                 | 4                                    | 4                                    |

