| Adagen® Lead-in Week -1                        |                        |                           | 2                 | 2               |                 |                 |              |                 | 4                                    | 4                                    |
| Adagen® Lead-in Week -2                        |                        |                           | 2                 | 2               |                 |                 |              |                 | 4                                    | 4                                    |
| Adagen® Dose Adjustment (if necessary)  |                        |                           |                   |                 |                 |                 |              |                 | 0                                    | 0                                    |
| Adagen® Lead-in Week -3 (if necessary)         |                        |                           | 2                 | 2               |                 |                 |              |                 | 4                                    | 4                                    |
| Adagen® Lead-in Week -4 (if necessary)         |                        |                           | 2                 | 2               |                 |                 |              |                 | 4                                    | 4                                    |
| Adagen® PK - Day 1 (0 hrs)                     | 3                      | 4                         | 2                 | 2               |                 | 2               | 3.5          | 4               | 20.5                                 | 20.5                                 |
| Adagen® PK - Day 2 (24 hrs)                    |                        |                           |                   |                 | 2               |                 |              |                 | 2                                    | 0                                    |
| Adagen® PK - Day 3 (48 hrs)                    |                        |                           |                   |                 | 2               |                 |              |                 | 2                                    | 2                                    |

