| EZN-2279 Dose Adjustment
(if necessary) |                           |                                 | Repeat Weeks T-5
through T-8 sampling |                    |                    |                    |                 |                    |                                      |                                      |
| Week T-9 - Day 57 (0 hrs)                          | 3                         | 4                               | 2  | 2                  |                    |                    | 3.5             | 4                  | 18.5                                 | 18.5                                 |
| Week T-9 - Day 58 (24 hrs)                         |                           |                                 |  |                    | 2                  |                    |                 |                    | 2                                    | 0                                    |
| Week T-9 - Day 59 (48 hrs)                         |                           |                                 |  |                    | 2                  |                    |                 |                    | 2                                    | 2                                    |
| Week T-9 - Day 60 (72 hrs)                         |                           |                                 |  |                    | 2                  |                    |                 |                    | 2                                    | 0                                    |
| Week T-9 - Day 61 (96 hrs)                         |                           |                                 |  |                    | 2                  |                    |                 |                    | 2                                    | 0                                    |
| Week T-9 - Day 62 (120 hrs)                        |                           |                                 |  |                    | 2                  |                    |                 |                    | 2                                    | 0                                    |
| Week T-9 - Day 63 (144 hrs)                        |                           |                                 |  |                    | 2                  |                    |                 |                    | 2                                    | 0                                    |

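### Appendix 2 blood volumes: the rows for patients 10 and older sum to 198 mL, not 244, and the under-10 figure of 178 mL is a scheduled total, not the maximum that Section 10.6.2.2 calls it

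*Protocol*

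**What the plan says.** Protocol Section 10.6.2.2, whose heading refers to the maximum total collection volume, says that over a patient's participation "the maximum amounts of venous blood that will be collected are listed in Appendix 2", and notes the limited PK sampling below age 10.

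Appendix 2 lists the draws visit by visit in two total columns, one per age group. The line at the end of the treatment period prints 244 mL (10 and older) and 178 mL (under 10). Maintenance follows below that line at 20.5 mL per visit.

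The columns differ only in the PK weeks. For patients under 10, Section 11.3.10 says that "PK sampling will be limited to trough samples and at 48 hours post dose", and Section 11.2.3.2 applies the same limit to the Adagen PK week. Sections 6.3.3 and 10.6.1 give blood volume and patient safety as the reasons.

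Several draws are conditional:

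- **EZN-2279 dose adjustment.** Section 11.3.8.1 instructs: "Return to Week T-5 (Section 11.3.5) and continue through weekly dosing for 4 weeks (T-5 through T-8". Appendix 2 has a row for this, reading "Repeat Weeks T-5 through T-8 sampling", with no volume in either total column.
- **Lead-in.** Section 11.2.2 lets the Adagen adjustment process repeat until the criteria are met. Appendix 2 lists four lead-in weeks; SAP Table 1 has a column for week 4 and beyond.
- **Repeat PK.** If the EZN-2279 dose is altered, Section 10.6.1 says "the full PK profile should be repeated not earlier than 4 weeks after adjustment of the dose of EZN-2279".

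A footnote to Appendix 2, marked on the dAXP, trough ADA, immunogenicity and Total columns, says that two 2 mL tubes are enough where those three samples coincide.

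**The concern.** There are two separate problems. First, the two printed totals cannot both be right for one table: they are 66 mL apart, while the listed draws differ by only a few small PK samples. Second, a figure presented as a maximum should not be exceeded by a patient managed exactly as the protocol directs, yet the under-10 total appears to contain only the scheduled rows.

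The second problem matters more. Sampling in young children was cut back because of blood volume, so this is the group for which investigators, ethics committees and families would rely on the figure.

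**Working it through.** **Step 1. Reproduce the printed totals.** All inputs are row totals from Appendix 2, in mL. Every conditional row that carries a volume is included.

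| Rows | 10 and older | Under 10 |
|---|---|---|
| Screening | 9 | 9 |
| Extra screening draw, once-weekly patients | 4 | 4 |
| Four lead-in weeks (4 × 4) | 16 | 16 |
| Adagen PK Day 1 | 20.5 | 20.5 |
| Adagen PK Days 2 to 7 | 6 × 2 = 12 | 1 × 2 = 2 |
| T-1 | 20.5 | 20.5 |
| T-3 | 6 | 6 |
| T-5, T-7, T-8 (11 + 4 + 4) | 19 | 19 |
| T-9, Day 57 | 18.5 | 18.5 |
| T-9, Days 58 to 63 | 6 × 2 = 12 | 1 × 2 = 2 |
| T-10, T-11 (6 + 4) | 10 | 10 |
| T-13, T-15, T-17, T-19 (11 + 4 + 11 + 4) | 30 | 30 |
| T-21 | 20.5 | 20.5 |
| **Sum** | **198** | **178** |
| **Printed** | **244** | **178** |

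Cross-check by column for the older group (number of samples × volume, in the order hematology, chemistry, dAXP, trough ADA, PK, immunogenicity, immunoglobulins, lymphocyte subsets): 8×3 + 8×4 + 19×2 + 19×2 + 12×2 + 6×2 + 4×3.5 + 4×4 = 198. Each row total also agrees with its own cells.

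The excess is 244 − 198 = 46 mL, and 46/198 = 23%. The age gap from the rows is 10 × 2 = 20 mL; the printed gap is 244 − 178 = 66 mL.

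**Step 2. Try to explain 244.** None of these variants gives it:

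- shared-tube footnote applied: 188
- three conditional 4 mL rows dropped: 186
- one T-5 to T-8 repeat added: 217; two repeats: 236
- one repeat plus a repeated PK profile: 229 to 233
- one maintenance visit added: 218.5; two: 239

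**Step 3. Test 178 as a maximum.** The printed figure is exactly the row sum with the dose-adjustment row empty, so it contains no repeat. One repeat costs T-5 + T-6 + T-7 + T-8 = 11 + 0 + 4 + 4 = 19 mL.

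- One repeat: 178 + 19 = 197 mL (+11%)
- Two repeats: 178 + 38 = 216 mL (+21%)

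**Step 4. Apply the footnote.** The row totals count three 2 mL samples at the five visits where immunogenicity, dAXP and ADA coincide (Adagen PK Day 1, T-1, T-3, T-10, T-21). Two tubes instead of three saves 5 × 2 = 10 mL, giving base totals of 188 and 168 mL. None of the repeated weeks includes immunogenicity, so the repeat still costs 19 mL.

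- One repeat, under 10: 168 + 19 = 187 mL (+5% over 178)
- Two repeats, under 10: 168 + 38 = 206 mL (+16%)

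**Step 5. Other draws outside 178.** Each lead-in week beyond the fourth adds 4 mL and each maintenance visit 20.5 mL. For patients 10 and older, a repeated full PK profile adds 6 × 2 = 12 mL, or 16 mL if the 0 h and 168 h troughs are extra draws.

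**The case against.** The strongest reply is that this is one mis-added cell in a table that hides nothing. The repeat has its own row directly below the T-5 to T-8 volumes, maintenance has its own row, and Section 10.6.2.2 points to Appendix 2 as a whole without naming the total line as a cap. That is fair as to visibility. It does not rescue the word maximum: the repeat row has no volume, and no figure in the table gives what a patient with a dose adjustment will have drawn.

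A second reply is that the excess in children is small and conditional. An adjustment needs failing values, a patient not considered fully detoxified, and agreement of three parties. The 178 mL also includes 12 mL of conditional draws. With the footnote applied, a child needing none of those has 168 − 12 = 156 mL scheduled and 156 + 19 = 175 mL after one repeat, still under 178. This stands as a description of many patients, but a maximum has to cover the others.

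A third reply is that the repeat PK profile adds little here. Under-10s have no full profile, and an adjustment at T-8 comes before T-9 sampling, so only a later adjustment would trigger a second profile. This is right, and it confines that item to patients 10 and older.

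Three stronger readings are tempting and not supported:

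- **That both totals leave out the repeats.** This is shown only for 178. The contents of 244 are unknown, and it exceeds the row sum plus one repeat (217) and plus two (236). Some sums do reach it, such as 198 + 2×19 + 2×4, but nothing in the documents says it was built that way.
- **That the error runs in the unsafe direction throughout.** For patients 10 and older, 244 overstates the listed draws. Only the under-10 figure understates what may be drawn.
- **That a safety limit is breached.** The documents give no volume limit per kilogram or per period, and a repeat spreads its 19 mL over four additional weeks.

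**Conclusion.** The point holds in two parts. The total for patients 10 and older does not follow from its own table: the rows give 198 mL against 244 printed. The under-10 total is added correctly, but it is a scheduled volume. One T-5 to T-8 repeat takes it to 197 mL on the printed rows, or 187 mL with shared tubes, an excess of 5% to 11% over the stated 178 mL.

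Loss of table rows in reading the document is an unlikely cause, because every week is present and the under-10 column, built on the same rows, reproduces exactly.

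The result assumes that a repeat carries the same draws as the original T-5 to T-8 visits, as Appendix 2 indicates. The text caps neither lead-in nor EZN-2279 adjustment cycles, so it yields no finite maximum; the schematics in Appendices 4 and 5 were not readable in the copy used, and a cap there is not ruled out.

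No endpoint, eligibility rule or analysis depends on these figures. It should be corrected because an operative section presents them as maximum draws, including for young children.

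**What to change.** In Appendix 2:

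- Reconcile 244 with the rows: print 198 mL as the scheduled volume, or state what else the figure contains. Replacing 244 by 198 while still calling it a maximum would not do, since one repeat already brings an older patient to 198 + 19 = 217 mL.
- Apply the shared-tube footnote consistently in the row totals and totals (188 and 168 mL), or explain why they ignore it.
- Enter 19 mL per repeat in the existing dose-adjustment row and 4 mL for each lead-in week beyond the fourth.
- Add the volume of any repeated PK profile for patients 10 and older (12 mL, or 16 mL with extra troughs).

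In Section 10.6.2.2, either state a maximum by age group that includes these items and says how maintenance is counted and how many adjustment cycles are assumed, or relabel the totals as scheduled volumes through Week T-21.

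The cost is a table correction and a sentence or two in an amendment. Any blood volume quoted in the consent form should be checked against the corrected table.

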## 10.7. Study Medication Administration and Compliance

### 10.7.1. Dosage and Administration

#### 10.7.1.1. Adagen®

Adagen® will be administered during the Adagen® Lead-in phase of the study. Patients will remain on his/her weekly Adagen® dose. The total weekly dosage will be consolidated to a once weekly dose regimen. This phase of the study will continue until the patient meets protocol criteria for dAXP levels and ADA activity.

For example, a 50kg patient on a dose of 15U/kg twice a week will have his/her dose consolidated to 30U/kg once weekly. The dose volume will be calculated as follows:

$$50 \text{ kg} \times 30\text{U/kg} \times 1 \text{ mL}/250 \text{ U} = 6.0 \text{ mL (1500 U)}$$

The date and time of each dose administered will be recorded.

#### 10.7.1.2. EZN-2279

EZN-2279 will be administered starting after completion of the Adagen® Lead-in phase. Patients will be transitioned to receive an equivalent dose of EZN-2279 as a weekly i.m. injection. Based upon 1 mg EZN-2279 containing ADA enzymatic activity of 150 U of Adagen®, the equivalent dose of EZN-2279 will be calculated as follows:

$$\text{Adagen® dose (U/kg)} \times 1\text{mg EZN-2279}/150\text{U Adagen®} = \text{EZN-2279 dose (mg/kg)}$$

For example, for a 50 kg patient on a dose of 30 U/kg of Adagen®:

$$\text{Adagen® 30 U/kg} \times \frac{1 \text{ mg EZN-2279}}{150 \text{ U Adagen®}} = 0.2 \text{ mg/kg EZN-2279}$$

$$50 \text{ kg} \times 0.2\text{mg/kg} \times 1 \text{ mL}/1.6 \text{ mg} = 6.25 \text{ mL (10 mg)}$$

The date and time of each dose administered will be recorded.

All patients will be observed for at least 1 hour after administration of EZN-2279 for doses administered at the study site through study Week T-9.

#### 10.7.2. Dose Adjustments

Adjustments of the dose and/or schedule of EZN-2279 or Adagen® may be required if a patient's trough plasma ADA activity is less than 15 µmol/h/mL and/or the trough dAXP level is greater than 0.02 µmol/mL for two or more consecutive assessments and compliance with the study drug regimen is confirmed and the patient is not considered fully detoxified. The Investigator, the sponsor, and Lead PI must agree upon all modifications in the dosing regimen for each patient before any changes are instituted.

The dose of Adagen® should not be adjusted more than once every 2 weeks and the dose EZN-2279 should not be adjusted more than once every 4 weeks to allow the effect of these changes on trough level of ADA to be manifested.

#### 10.7.3. Treatment Delays

EZN-2279 or Adagen® will be administered weekly ± 1 day. The PI, after upon consultation with Leadiant Biosciences and Lead PI, may elect to delay or withhold a dose if the clinical condition of the patient warrants such action. The PI, Leadiant Biosciences, and Lead PI must agree upon all modifications in the dosing regimen for each patient before any changes are instituted.

#### 10.7.4. Assessment of Study Medication Compliance

Compliance will be assured by having the study drug administered under the supervision of the PI and/or designated site staff members while the patient is at the clinic/study site during the visit(s). Administration of the study drug must be recorded in source documents. For EZN-2279 Treatment Week 12, the patient is permitted to self dose at home, but enough drug will be dispensed along with diary cards which become part of the patient source documentation.

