#### 6.3.1. Primary Endpoint

The primary endpoint is the percentage of patients achieving metabolic detoxification, assessed from trough dAXP samples obtained at Weeks T-15, T-17, T-19, and T-21. Metabolic detoxification will be defined as a trough dAXP concentration equal to or below 0.02  $\mu\text{mol/mL}$ .

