#### 11.3.14. Day 85 (Week T-13)

On Day 85 ( $\pm$  1 day) the patient will return to the study site and have the following procedures performed:

- Physical examination
- Height and weight for growth assessment
- Performance status
- Vital Signs
- Safety Lab
  - Hematology

- Chemistry
- Adverse event assessment
- Assessment of infectious complications and hospitalizations
- Assessment of concomitant medications and procedures since last study visit

Blood samples will be obtained 15 to 30 minutes prior to administration of EZN-2279 for:

- dAXP
- Trough ADA activity

The patient will receive his/her dose of EZN-2279 after all procedures and laboratory blood draws have been completed.

If the patient will self-administer the Week T-14 dose of EZN-2279, the dose will be dispensed with a dosing diary card and administration instructions.

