#### 11.3.16. Day 99 (Week T-15)

On Day 99 ( $\pm$  1 day) the patient will return to the study site and have the following procedures performed prior:

- Adverse event assessment
- Assessment of infectious complications and hospitalizations
- Assessment of concomitant medications and procedures since last study visit

Blood samples will be obtained 15 to 30 minutes prior to administration of EZN-2279 for:

- dAXP
- Trough ADA activity

The patient will receive his/her dose of EZN-2279 after all procedures and laboratory blood draws have been completed.

If the patient will self-administer the Week T-16 dose of EZN-2279, the dose will be dispensed with a dosing diary card and administration instructions.

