#### 11.3.21. Day 134 (Week T-20)

On Day 134 ( $\pm$  1 day) the patient will receive his/her dose of EZN-2279. The dose may be given at the study site or self-administered by the patient.

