#### **11.4. EZN-2279 Maintenance Period**

As part of standard clinical care, the following evaluations will be performed during visits approximately every 3 months (13 weeks  $\pm$ 3 weeks) until study completion. For example, based upon the start of EZN-2279 treatment (Day 1, Week T-1), maintenance visits would be scheduled to occur on Weeks 34 (Cycle 1), 47 (Cycle 2), 60 (Cycle 3), 73 (Cycle 4), 86 (Cycle 5), 99 (Cycle 6), 112 (Cycle 7), 125 (Cycle 8), 138 (Cycle 9), 151 (Cycle 10), 164 (Cycle 11), 177 (Cycle 12), 190 (Cycle 13)  $\pm$ 3 weeks from start of EZN-2279 treatment.

The patient will have the following procedures performed at each maintenance visit prior to EZN-2279 dosing:

- Physical examination
- Height and weight for growth assessment
- Performance status
- Vital Signs
- Safety Lab
  - Hematology
  - Chemistry
  - Urinalysis
- Other labs – blood samples will be obtained 15 to 30 minutes prior to dosing for:
  - dAXP
  - Trough ADA activity
  - B-, T-, and NK-lymphocyte subset analysis
  - Quantitative immunoglobulins
  - EZN-2279 antibody titers (i.e., neutralizing and binding antibodies) and anti-PEG antibodies
- Adverse event assessment
- Assessment of infectious complications and hospitalizations
- Review of EZN-2279 administration diary card and returned vials for assessment of treatment compliance
- Assessment of concomitant medications and procedures since last study visit

- Assessment of overall survival

An appropriate supply of EZN-2279 will be dispensed along with a medication compliance diary card. Note that it is not necessary to dispense a full 13 week supply during a maintenance visit; quantities of EZN-2279 dispensed will be at the discretion of the Investigator based upon the patient's proximity to the study site and medication compliance.

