10.4 Screening, Baseline and Study Weeks

No windowing schemes will be applied to the data. For by-visit summaries, if there are multiple assessments at a post baseline visit then the last non-missing assessment at that visit will be used for the summary. This includes assessments at the scheduled and unscheduled visits. For Patients who withdraw from the study, data at the early termination visit will be excluded from the by-visit summaries but will be included in the endpoint summaries.

Screening is defined as the last measurement for a variable before the initial dose of Adagen[®] study drug. With the exception of adverse events and medications, assessments collected at the screening visit are associated with the screening period because Adagen[®]

is not administered until all procedures are complete. Adverse events and medications starting on the day of the first dose of Adagen[®] are associated with Adagen[®] treatment.

Baseline is defined as the last measurement for a variable before the initial dose of EZN-2279 study drug, and is only used as the starting point for efficacy endpoints. With the exception of adverse events and concomitant medications, assessments collected at EZN-2279 Day-1 (Week T-1) are associated with Adagen[®] treatment because EZN-2279 is not administered until all procedures are complete. Adverse events and concomitant medications starting on the day of the first dose of EZN-2279 are associated with EZN-2279 treatment.

With regard to screening and baseline determination, assessments falling exactly on the date of the first dose of each study medication will be considered pre-dosing for that medication with the exception of adverse events and concomitant medications, which will be associated with the respective study drug.

Missing data will not be imputed.

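### All four primary troughs follow a dose that may be given at home; the protocol's sections disagree on home dosing, and no SAP rule ties a primary sample to a verified dose or to the time since it

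*Protocol*

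**What the plan says.** **Where doses are given.** Protocol 10.7.4 states the general rule, "Compliance will be assured by having the study drug administered under the supervision of the PI and/or designated site staff members", and then one exception: "For EZN-2279 Treatment Week 12, the patient is permitted to self dose at home". The visit schedule is wider. Sections 11.3.13, 11.3.15, 11.3.17, 11.3.19 and 11.3.21 (Weeks T-12, T-14, T-16, T-18 and T-20) each say "The dose may be given at the study site or self-administered by the patient". The preceding visits provide for it; at T-15, for example: "If the patient will self-administer the Week T-16 dose of EZN-2279, the dose will be dispensed with a dosing diary card and administration instructions".

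**What is measured.** The primary endpoint (Protocol 6.3.1) is "assessed from trough dAXP samples obtained at Weeks T-15, T-17, T-19, and T-21". Trough ADA activity, a secondary endpoint, uses the same four weeks. SAP 6.2 and 6.3.1 count a patient as maintained only if all four samples meet the target.

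**What is checked.** Protocol 11.4 lists, for maintenance visits, "Review of EZN-2279 administration diary card and returned vials for assessment of treatment compliance". The visit lists for T-13, T-15, T-17, T-19 and T-21 have no such item. Samples are timed 15 to 30 minutes before the next dose, not from the previous one. Protocol 10.7.3 sets dosing at weekly plus or minus 1 day, and Section 11.3 puts plus or minus 1 day on each scheduled day. SAP 10.4 adds "No windowing schemes will be applied to the data", and the completer population in SAP 4.3 carries no adherence criterion.

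**The concern.** Two sites could act differently and each point to the protocol: one following 10.7.4 would give the T-14 to T-20 doses under supervision, and one following Section 11.3 could send them home. Those are the doses on which every primary and ADA responder sample depends.

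A trough is interpretable only if the previous dose was given and the time since it is known. Here the previous dose may be unsupervised, no scheduled step reviews its diary card at the visit where the sample is drawn, and the analysis plan does not use the recorded time. A short interval can flatter a reading. A late visit or a missed injection can make an adequate regimen look inadequate. Under a four-of-four rule with six evaluable patients, one such sample can change the headline proportion.

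**Working it through.** The plan gives no figure of its own to reproduce; both documents say sample-size calculation does not apply. The check covers the schedule, the interval, and the likely size of a shift.

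**1. Schedule.** Day = 7 x (week - 1) + 1 reproduces the protocol's visit days.

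| Primary sample | Day | Preceding dose | Day | Home dosing under 11.3 |
|---|---|---|---|---|
| T-15 | 99 | T-14 | 92 | allowed |
| T-17 | 113 | T-16 | 106 | allowed |
| T-19 | 127 | T-18 | 120 | allowed |
| T-21 | 141 | T-20 | 134 | allowed |

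So 4 of 4 primary samples follow a home-eligible dose. Counting T-12, 5 of 21 doses may be given at home.

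**2. Interval from dose to sample.**
- Windows applied separately to dose and visit: shortest (99 - 1) - (92 + 1) = 5 days; longest (99 + 1) - (92 - 1) = 9 days.
- Protocol 10.7.3 read as a dosing interval: 6 to 8 days.
- Home dose missed, separate windows: (99 - 1) - (85 + 1) = 12 to (99 + 1) - (85 - 1) = 16 days since the T-13 dose.

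**3. Effect on ADA activity.** Assumptions: first-order decline, steady state on weekly dosing, and the EZN-2279 half-lives in Protocol 5.4 (dog 128-154 h, rat 49-61 h). The documents give no human value. Let a = 2^(24/t½) be the one-day factor and r = 2^(-168/t½) the one-week factor. When only the home dose and the visit move by a day, the earlier doses shift by 24 h and the last dose by 48 h. Relative to a 7-day trough:

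- 5 days: a²(1 - r) + a·r
- 9 days: (1 - r)/a² + r/a
- missed home dose, visit on its nominal day: r

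For 128 h, a = 1.139 and r = 0.403. At 5 days this gives 1.297 x 0.597 + 1.139 x 0.403 = 1.23. For 154 h, a = 1.114 and r = 0.470, giving 1.241 x 0.530 + 1.114 x 0.470 = 1.18.

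| | Dog 128 h | Dog 154 h | Rat 49 h | Rat 61 h |
|---|---|---|---|---|
| 5 days | 1.23 | 1.18 | 1.92 | 1.66 |
| 9 days | 0.81 | 0.85 | 0.53 | 0.61 |
| Missed dose | 0.40 | 0.47 | 0.09 | 0.15 |

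Using dog half-lives and the target of 15 µmol/h/mL:
- A true 7-day trough of 15/1.23 = 12.2 to 15/1.18 = 12.7 would read 15 at 5 days.
- After a missed dose, a patient whose usual trough is below about 15/0.47 = 32 to 15/0.40 = 37 would read under 15.
- On the 6-to-8-day reading the factors are a and 1/a: 11-14% high, 10-12% low.

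**4. Effect on dAXP.** The documents give no dAXP kinetics, so no figure can be attached to the primary endpoint.

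**5. Effect on the proportion.** Exact (Clopper-Pearson) 95% intervals with n = 6: 6/6 = 100% (54.1-100%); 5/6 = 83.3% (35.9-99.6%).

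**The case against.** **Existing safeguards.** The date and time of each dose are recorded (Protocol 10.7.1.2). Diary cards are source documents (10.7.4). Staff must verify compliance and document lapses (10.9), and monitors compare source with case report forms (14.6.1). Dose delays and omissions are to be described (13.2.3.3). SAP 5.8 has the clinical team review deviations, including assessment timing. A reader might infer that a missed or mistimed home dose would go undetected. The documents do not support that. What stands is narrower: diary review is not scheduled at the primary visits, and none of these records decides how a primary sample is treated.

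**The percentages.** They concern plasma ADA, a secondary endpoint. It is tempting to carry them over to dAXP, but nothing in the documents allows it. Scaling the whole trough by 48 h would give larger dog-based shifts (24-30% high, 19-23% low), but that ignores drug remaining from earlier on-schedule doses.

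**False passes.** A reader might infer that one early sample could create an ADA responder. The four-of-four rule prevents this unless that visit is the only one with a true trough below target: favourable timing is needed at every such visit. A false failure needs only one bad sample.

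**Windows.** The SAP's no-windowing statement governs visit summaries, and a visit window would not control the dose-to-sample interval anyway. The one-day tolerance also applies to supervised doses, so it is not peculiar to home dosing. Both points stand. Home dosing matters because the start of the interval rests on a diary that no listed step reviews at that visit.

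**Conflict.** Section 10.7.4 does not expressly forbid home dosing in other weeks. It does state supervision as the rule and names a single exception, so the passages still need reconciling.

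**Conclusion.** The concern holds in this limited form. The overlap is exact: every primary trough follows a dose that Section 11.3 lets the patient give at home, while 10.7.4 names only Week 12. The data needed to check the dose are collected, but no SAP rule links a primary sample to a verified dose or an acceptable interval.

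The direction of any bias is not fixed, and the effect on dAXP is unknown. For ADA, the dog-based shifts of roughly a fifth either way are the extremes of the 5-to-9-day reading; they shrink on the 6-to-8-day reading and grow with the rat half-lives. A missed home dose is the larger risk and points towards false failure. If one occurred, the result among six evaluable patients would fall from 6/6 to 5/6 and the lower confidence limit from 54% to 36%. All of the ADA figures assume that animal half-lives carry over to patients.

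This should be corrected. It is not a reason to doubt the endpoint itself.

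**What to change.** 1. **Protocol.** Reconcile 10.7.4 with Section 11.3 on when home dosing is allowed, and state whether the one-day tolerance applies to the dosing interval or separately to each scheduled day. Which rule is right is for the sponsor and investigators.
2. **Visits.** Add the diary and vial review already used in maintenance to T-13, T-15, T-17, T-19 and T-21.
3. **SAP, derivation.** From recorded times, derive and list the dose-to-sample interval for each primary sample, and flag whether the preceding dose was verified.
4. **SAP, analysis.** Keep the all-samples, four-of-four analysis as primary. Add a sensitivity analysis of dAXP and ADA responders limited to samples 7 ± 1 days after a documented dose.
5. **SAP, classification.** State in advance how patients with fewer than four qualifying samples are classified, for example shown both as non-responders and on their available samples. Report samples after missed or unverified doses separately. Without this, the restricted analysis would drop the samples most likely to fail.

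The cost is amendment wording, a few minutes at five visits and one extra table. No dose or clinical rule changes as a result of the analysis steps.
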